## AMENDMENT HISTORY

### Amendment 2

The primary purpose of this amendment is to close the study. The procedures described in this amendment supersede those of the original protocol and site memorandum.

Description of Change	Brief Rationale	Section(s)

Added a new section with procedures specifying the study closure process, which includes the following:
 
 
• Participants will be offered the option to receive a supplemental final dose of casirivimab+imdevimab 1200 mg SC
 
• All participants, including those who do not consent to receive the optional final dose, will have a follow-up (end-of-study) telephone visit approximately 3 months from their last dose of investigational drug (casirivimab+imdevimab or placebo) to monitor safety
 
• Participants with suspected COVID-19 may have an optional visit to evaluate signs and symptoms and to receive local and central laboratory testing for SARS-CoV-2
 
• For participants who are SARS-CoV-2 positive, additional weekly visits can optionally occur until 2 consecutive negative RT-qPCR tests are obtained
 
• Safety collection will be broadened from original protocol to include treatment-emergent AEs considered by the investigator to be unrelated to baseline conditions and unrelated to treatments for baseline conditions.
 
• Participants will be monitored for at least 60 minutes after receiving study drug
 
• Sites will ensure that an additional discussion about the potential risks and benefits to the participant and fetus is discussed as part of re-consent for participants who become pregnant during the study
 
• A modified statistical analysis plan has been summarized for participants who have already enrolled in the study
 
	
To provide guidance to US sites regarding study close-out procedures.
	
Protocol Amendment 2 Procedures  Table 2 Schedule of Events for Study Close-Out (Applies to All Enrolled Participants Per Protocol Amendment 2)  Section 9.1.2 Footnotes for the Schedule of Events (Protocol Amendment 2)

## Site Memorandum

This section describes changes to study conduct that were implemented by a site memorandum issued on 21 October 2021.

Original Protocol	Change / Additional Measures
No Scheduled Safety Labs	Measure absolute neutrophil count, platelet count, hemoglobin, ALT, AST, total bilirubin, and creatinine at the baseline visit as well as study visits days 29, 85 and 169
Monitor for 15 minutes after first dose	Monitor for 60 minutes after administration of study drug
Report treatment emergent adverse events (TEAEs) that are grade $\geq 3$ in severity	Report all clinical and laboratory TEAEs that are not related to the patient's underlying (non-COVID) disease and/or not related to treatments for the underlying conditions

**LIST OF ABBREVIATIONS AND DEFINITIONS OF TERMS**

ADA	Anti-drug antibody
AE	Adverse event
AESI	Adverse event of special interest
CI	Confidence interval
CRF	Case report form (electronic or paper)
CRO	Contract research organization
EC	Ethics Committee
EDC	Electronic data capture
FDA	US Food and Drug Administration
GCP	Good Clinical Practice
HSCT	Hematopoietic stem cell transplantation
ICF	Informed consent form
ITT	Intention-to-treat
ICH	International Council for Harmonisation
IRB	Institutional Review Board
IV	Intravenous
IVIG	Intravenous immunoglobulin
mITT	Modified intention-to-treat
NAb	Neutralizing antibody
NCI-CTCAE	National Cancer Institute-Common Terminology Criteria for Adverse Events
NP	Nasopharyngeal
PCSV	Potentially clinically significant value
PK	Pharmacokinetic
Q4W	Every 4 weeks
Q12W	Every 12 weeks
Regeneron	Regeneron Pharmaceuticals, Inc.
RBQM	Risk-Based Quality Monitoring
SAE	Serious adverse event
SAP	Statistical analysis plan
SAS	Statistical Analysis System
SC	Subcutaneous
SCIG	Subcutaneous immunoglobulin
SOC	System organ class
SUSAR	Suspected unexpected serious adverse reaction
TEAE	Treatment-emergent adverse event

## **CLINICAL STUDY PROTOCOL SYNOPSIS**

As of protocol amendment 2 this study will close. Please refer to [Protocol Amendment 2 Procedures](#) for further details.

## PROTOCOL AMENDMENT 2 PROCEDURES

Study R10933-10987-COV-2176 will be terminated early by the Sponsor due to evidence surrounding variants of concern and reduced neutralization potency of casirivimab+imdevimab against the Omicron variant. The study is not being terminated due to any safety concerns, nor from any data obtained in this study.

The procedures described in amendment 2 should be implemented immediately at sites that have participants who are currently enrolled in the study.

### Optional Dose

The Sponsor believes that casirivimab+imdevimab may continue to serve as an important pre-exposure prophylaxis therapeutic among immunocompromised individuals in regions where Omicron is not the dominant variant or in regions where Omicron prevalence subsides. For this reason, participants will have the option to receive a 1200 mg SC dose of casirivimab+imdevimab as a final study dose. This optional dose may be administered to all participants regardless of treatment assignment at randomization. However, participants will not be eligible to receive this dose if they have already received casirivimab+imdevimab as post-infection treatment.

Participants will be asked to return to the site for an unscheduled visit, during which they will be asked to consent to protocol amendment 2 and receive the final optional dose, if desired. This visit to receive the final optional dose should occur approximately 4 weeks after the most recent dose. Note that consent may be obtained remotely prior to this visit, if available and allowable by the study site.

### Procedures in the Event of Suspected COVID-19

Participants with suspected COVID-19 may undergo an optional visit to evaluate symptoms by a study clinician (investigator or designee) and to undergo laboratory testing of SARS-CoV-2, as detailed in the new schedule of events ([Table 2](#)). This optional visit should occur as soon as possible (**within 48 hours of symptom onset, if feasible**). Note that clinician assessment of sign or symptoms may occur remotely. If remote assessment is performed, a confirmatory site visit for laboratory testing of SARS-CoV-2 can optionally occur after a clinician deems that the signs or symptoms are related to COVID-19.

*Clinical Evaluation.* Signs and symptoms will be evaluated by a clinician (investigator or designee, evaluation may occur remotely) as described below. If the clinician confirms that at least one sign or symptom is potentially related to COVID-19, samples may be collected to perform both **local** and **central** testing for SARS-CoV-2 infection.

*Laboratory Testing of SARS-CoV-2.* Local testing must be performed by RT-PCR using local sample collection and assay standards. A nasopharyngeal (NP) swab sample is the preferred sample type, but other samples (eg, nasal, oropharyngeal, saliva) adhering to local standards are acceptable. An additional NP swab sample will be collected for the purposes of central RT-qPCR testing. The samples will be collected prior to any administration of post-infection treatment (described below). The qualitative result of the central RT-qPCR will be reported back to the corresponding study site.

SARS-CoV-2 viral genome sequencing will be performed using NP swab samples collected during the study that have been confirmed positive by RT-qPCR at the central laboratory.

*Documentation of Clinical Evaluation.* For each symptom, the start (onset) date, end date, and severity will be recorded (mild, moderate, severe) in the participant's medical record (source document). It is important to record this information in the source document, to ensure that the temporal dimensions of each sign or symptom are captured.

The following information may subsequently be recorded in EDC as applicable:

- The sign or symptom, with start (onset) calendar date, end calendar date, and severity (mild, moderate, severe)
- Confirmatory local RT-PCR test result and date of sample collection
- Confirmatory central RT-qPCR test result and date of sample collection
- Weekly central RT-qPCR test results and dates of sample collection
- Record of any post-infection treatment with casirivimab+imdevimab administered

Note that any sign or symptom considered by the investigator to be unrelated to baseline conditions and unrelated to treatments for baseline conditions will also be recorded and used for safety evaluation.

*Post-Infection Treatment.* Participants with confirmed positive SARS-CoV-2 RT-PCR will be eligible for post-infection treatment (as described in Section 6.4.4) at any time prior to receipt of the optional 1200 mg SC dose (eg, during the 4 weeks between receipt of the last protocol-defined dose and the optional 1200 mg SC dose). Once this optional dose has been administered, post-infection treatment will no longer be offered. Likewise, any participant who receives post-infection treatment will not be eligible to receive the optional 1200 mg SC dose.

*Participants with Positive SARS-CoV-2 RT-PCR.* Participants with a positive SARS-CoV-2 RT-PCR may have additional assessments and sample collections, during unscheduled visits every 7 days ( $\pm 1$  day) for central laboratory RT-qPCR analysis until 2 consecutive negative test results are obtained:

- NP swab samples for RT-qPCR
- COVID-19 signs and symptoms evaluated by the investigator or designee
- Information regarding COVID-19-related medically-attended visits (MAVs; defined in Section 9.2.4.3)

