### End-of-Study Visit

All participants, including those who do not consent to receive the optional final dose, will have a follow-up (end-of-study) telephone visit approximately 85 days (3 months) from their last dose of investigational drug (casirivimab+imdevimab or placebo) to monitor safety. Study assessments for the 3-month follow-up visit will be limited to the collection of targeted adverse events, as detailed in the new schedule of events (Table 2).

Sites will ensure that an additional discussion about the potential risks and benefits to the participant and fetus is discussed as part of re-consent for participants who become pregnant during the study.

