### 3.3.2. Summary of Risks

**Identified Risks.** As with other protein therapeutics, hypersensitivity reactions, including acute infusion-related reactions (intravenous administration) or injection site reactions (subcutaneous administration), may develop immediately or within a few hours to days after study drug administration. Hypersensitivity reactions, including infusion-related reactions or injection site reactions, have been observed in study participants who received casirivimab+imdevimab during ongoing clinical trials.

**Potential Risks.** The potential risks of casirivimab+imdevimab are the clinical consequences of immunogenicity and embryo-fetal toxicity.

Protein therapeutics carry the potential risk of an immunogenic response in the form of anti-drug antibody (ADA) and neutralizing antibody (NAb) development following administration, with possible consequences on safety and efficacy. Therefore, blood samples for immunogenicity assessment will be collected during the studies.

Reproductive and developmental toxicology studies have not been conducted, and the effects of casirivimab, imdevimab, or casirivimab+imdevimab combination therapy on the fetus and reproductive organs in males and females are unknown. There is also currently limited clinical experience in the use of casirivimab, imdevimab, or casirivimab+imdevimab combination therapy in females who are pregnant or breastfeeding.

Human IgG1 antibodies are known to cross the placental barrier and are present in breast milk. Casirivimab and imdevimab combination therapy therefore has the potential to be transferred from the mother to the developing fetus or a breastfed child. Given the high affinity and specificity of casirivimab+imdevimab, off-target pharmacological effects are not anticipated in either the mother or the fetus, and no off-target binding of casirivimab or imdevimab was observed in any of the human or monkey tissues evaluated *ex vivo* in tissue cross-reactivity studies. However, it is unknown whether the potential transfer of casirivimab+imdevimab combination therapy provides any treatment benefit or risk to the developing fetus or a breastfed child.

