#### **6.4.4. Post-Infection Treatment for Participants with Confirmed Positive SARS-CoV-2 RT-PCR**

Participants with a confirmed positive SARS-CoV-2 RT-PCR at any time during the study (local, central, or documented outside of the study) should be treated with standard of care per local practices and per the investigator's judgment. In addition, casirivimab+imdevimab may be offered to the participant as post-infection treatment if medically appropriate in the investigator's judgment.

If post-infection treatment with casirivimab+imdevimab is deemed medically appropriate, the treatment should be provided through the most expeditious mechanism available. To this end, casirivimab+imdevimab may be given through mechanisms outside of the study in regions where it is approved or authorized. Where regionally approved or authorized, casirivimab+imdevimab should be administered at the approved or authorized dose.

For participants who are able to receive post-infection care at a study site, casirivimab+imdevimab may also be offered to the participant as part of the study. This mechanism can be used, for example, if casirivimab+imdevimab is not regionally approved or authorized for treatment of SARS-CoV-2 infection, or if treatment cannot be made available in an expeditious manner via the approved or authorized mechanisms.

The following investigational dose levels will be offered as part of the study, and may be provided if medically indicated in the investigator's judgement:

- Not hospitalized due to COVID-19 and does not require supplemental oxygen or an increase in baseline oxygen flow rate due to COVID-19: **1200 mg** (600 mg per mAb), administered either intravenously or subcutaneously
- Hospitalized due to COVID-19 and does not require supplemental oxygen due to COVID-19, or requires low-flow supplemental oxygen due to COVID-19: **2400 mg** (1200 mg per mAb), administered intravenously
- Hospitalized due to COVID-19 and requires either high-intensity supplemental oxygen due to COVID-19 or requires mechanical ventilation due to COVID-19: **8000 mg** (4000 mg per mAb), administered intravenously

If feasible, treatment with casirivimab+imdevimab should be provided within 48 hours after a positive RT-PCR result is obtained.

Administration of post-infection treatment with casirivimab+imdevimab will not require unblinding of the participant's randomization assignment (Section 8.7).

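### Amendment 2 keeps in-study post-infection casirivimab+imdevimab, but its close-out schedule requires no vital signs around that dose and footnote 1 leaves it out of the 85-day clock

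*Protocol*

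**What the plan says.** Amendment 2 closes the study but keeps post-infection treatment. Under Protocol Amendment 2 Procedures, participants with a confirmed positive RT-PCR "will be eligible for post-infection treatment (as described in Section 6.4.4) at any time prior to receipt of the optional 1200 mg SC dose". Section 6.4.4 says that, for those who can be treated at a study site, "casirivimab+imdevimab may also be offered to the participant as part of the study". The levels are 1200 mg IV or SC for participants not hospitalized for COVID-19, and 2400 mg or 8000 mg IV, depending on oxygen need, for those who are. SAP Section 4.4.2 repeats them.

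This dose and the optional closing dose exclude each other: "any participant who receives post-infection treatment will not be eligible to receive the optional 1200 mg SC dose".

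Table 1, now marked as no longer applicable, had a Post-Infection Treatment Visit column. Table 2, copied as SAP Table 4, has three columns: the visit for the optional dose, optional confirmatory visits for suspected COVID-19, and the end-of-study telephone call. Footnote 4 in Section 9.1.2 asks for vital signs before and at least 60 minutes after study drug, and is attached to the optional-dose visit only.

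The Amendment History adds a general statement: "Participants will be monitored for at least 60 minutes after receiving study drug". The End-of-Study Visit text places the closing call "approximately 85 days (3 months) from their last dose of investigational drug". Footnote 1 in Section 9.1.2 defines that dose as the optional dose or, for those who do not receive it, the final assigned dose.

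**The concern.** Section 3.3.2 lists hypersensitivity among the identified risks, "including acute infusion-related reactions (intravenous administration) or injection site reactions (subcutaneous administration), may develop immediately". Checks around a dose exist for that risk. The live schedule requires them for an optional 1200 mg SC dose in a participant who has not had post-infection treatment. It requires none for a post-infection dose, which may be IV and may be larger, in an infected, immunocompromised participant. Nothing in Amendment 2 explains the difference, which suggests that the treatment visit was left out when the schedule was shortened.

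The closing call has a related problem. A participant treated after infection cannot receive the optional dose, so footnote 1 counts the 85 days from the last assigned dose, which came before the post-infection dose. Safety follow-up after the most recent active dose is then shorter than the End-of-Study Visit text implies.

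**Working it through.** **Schedule comparison.** The plan gives no figure to reproduce, so the first step is to set Table 1's Post-Infection Treatment Visit beside what now applies.

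| Item | Table 1 visit (superseded) | Live text for this dose |
|---|---|---|
| Treatment given | Marked | No Table 2 row. Section 8.9 requires any treatment up to the final visit to be recorded; Section 8.8.3 requires drug dispensed to be accounted for |
| Concomitant medications | Marked | Not tied to this dose in Table 2; required by Section 8.9 |
| Adverse events | Grade ≥3 marked | Not tied to this dose in Table 2; Section 10.1.1 requires assessment at each visit |
| SAEs | Marked | Not tied to this dose in Table 2; Section 10.1.3 requires SAEs and AESIs to be reported within 24 hours |
| Vital signs | Comprehensive set, before dosing (Section 9.1.1, footnote 6) | None required |
| Post-dose observation | None; the 15 minutes in footnote 6 applies to day 1 | 60 minutes after study drug (Amendment History, Site Memorandum), probably covering this dose |

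Of the five items Table 1 marked, four remain required by text outside the table. Vital signs do not.

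The confirmatory visit does not fill the gap. It has a comprehensive vital-sign row, but it is timed to symptom onset and is optional for site and participant (Section 9.1.2, footnote 6). It is also diagnostic: "The samples will be collected prior to any administration of post-infection treatment". The provision allowing confirmation and treatment on one day is a Table 1 footnote that was not carried into Section 9.1.2. Amendment 2 does list "Record of any post-infection treatment with casirivimab+imdevimab administered" among items that may be entered in EDC, but that documents the dose rather than checking the participant.

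**Closing call.** If the post-infection dose is given d days after the last assigned dose, footnote 1 leaves 85 − d days to the call.
- d = 28 (nominal day of the optional-dose visit): 85 − 28 = 57 days.
- d = 35 (late edge of that visit's ±7-day window): 85 − 35 = 50 days.
- A participant who receives the optional dose has 85 days after it.

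A participant who declines the optional dose stays eligible for post-infection treatment, so d can exceed 35.

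**How many participants.** Inputs are 66 enrolled (about 66/4 = 16.5 per arm) and the six-month incidences in protocol Table 6: 4.02%, 1.628%, 1.829% and 2.231%. Six months is taken as 168 days and all 66 as still at risk, which makes this an upper bound at those rates.
- Sum of rates: 4.02 + 1.628 + 1.829 + 2.231 = 9.708%.
- Expected cases in six months: 16.5 × 0.09708 = 1.602.
- Over 28 days, before the optional dose: 1.602 × 28/168 = 0.267.
- Over 85 days, if everyone declines it: 1.602 × 85/168 = 0.810.

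These are cases, not doses. The documents do not give the share that would be treated in the study, so 10% to 50% is assumed. The chance of at least one dose is 1 − exp(−expected doses).
- Low: 0.267 × 0.10 = 0.027 doses; chance 2.6%.
- High: 0.810 × 0.50 = 0.405 doses; chance 33.3%.
- Incidence doubled (assumption), low: 0.534 × 0.10 = 0.053 doses; chance 5.2%.
- Incidence doubled (assumption), high: 1.621 × 0.50 = 0.810 doses; chance 55.5%.

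**The case against.** The strongest reply is that little is missing. Only Table 1 was withdrawn; Sections 8 to 10 remain in force and still require the dose, concomitant medications and adverse events to be captured, and Section 8.4.1.1 requires emergency equipment to be at hand. Table 1's vital signs for this visit were taken before dosing, so they would not have detected a reaction to it. If the newer 60-minute monitoring covers this dose, post-dose observation is now stronger than Table 1 required. Reactions that appear within hours to days are not affected by whether a call comes 57 or 85 days later. The 2400 mg and 8000 mg doses apply only to participants hospitalized for COVID-19.

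Most of this stands, and it rules out two stronger readings. A reader might infer from Table 2 that safety capture for this dose has disappeared; the sections listed in the comparison show otherwise. A reader might also infer that the plan is now weaker than Table 1 in every respect; on post-dose observation it probably is not.

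Two things survive. First, none of the remaining provisions requires a vital-sign measurement around this dose. The 60-minute statement does not name it, and the meaning of study drug is unsettled: Table 1 applied a study-drug footnote to this dose, while Section 8.3.2.1 lists receiving post-infection treatment as a reason to stop study drug. Second, footnote 1 and the End-of-Study Visit text conflict for these participants, even though that conflict has no bearing on acute reactions.

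**Conclusion.** The point holds in a narrow form. A site following Table 2 and its footnotes takes no required vital signs around an in-study post-infection dose, and times the closing call from an earlier dose. Table 1 required a pre-dose set here, and Table 2 requires sets before and after the optional 1200 mg SC dose.

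Probably zero or one participant is affected: 0.03 to 0.41 expected in-study doses at planning rates, or 0.05 to 0.81 if incidence doubles. Both ranges rest on the assumed 10% to 50% in-study share and on treating all 66 as at risk. Supply outside the study (Section 6.4.4) and reduced potency against Omicron both point toward the low end. No estimate, interval or test changes. This is a cheap improvement for participant safety, at the bottom of the minor range.

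**What to change.** Add one footnote or column to protocol Table 2 for in-study post-infection doses:
- extend footnote 4 to them, with vital signs before and at least 60 minutes after administration;
- state that the 60-minute monitoring applies;
- mark the Amendment 2 TEAEs and the SAEs at that visit.

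The post-dose vital signs would be a new requirement, not a restoration of Table 1.

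Amend footnote 1 so that the 85 days run from the post-infection dose when that is the last casirivimab+imdevimab dose given in the study, in line with the End-of-Study Visit text. SAP Table 4 follows as a copy. Dose levels and eligibility stay as they are.

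The cost is up to an hour of observation at a visit the participant already attends, a little more data collection, and a closing call that moves later by the interval between the two doses, about 28 days for a dose given on day 28.
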